### **2.3.2 Known Potential Benefits**

Participants may or may not benefit from receiving the investigational drug by experiencing decreased pain and improved functionality. In the absence of any approved TMD medication, this search for an efficacious, safe, and affordable treatment may benefit many TMD patients in the future. In addition, the proposed clinical trial will advance our knowledge of the role of the adrenergic system in the pathogenesis of TMD.

## **2.4 Study Objectives**

### **2.4.1 Primary Objective**

The primary objective is to investigate the efficacy of extended-release propranolol compared with placebo in the reduction of a pain index (defined in Section 2.5.1) in participants with TMD at week 9 of treatment (at Visit 4).

### **2.4.2 Secondary Objectives**

The secondary objectives are as follows:

- To investigate gene-by-treatment group interaction to determine whether the efficacy of extended-release propranolol in the reduction of the pain index varies according to participants' polymorphisms in the coding region of the *COMT* gene.
- To investigate the efficacy of extended-release propranolol compared with placebo using secondary endpoints, namely: (1) additional pain ratings; (2) examiner assessments of experimental pain sensitivity; (3) participant ratings of physical function, emotional function, and global impression of change; (4) occurrence of symptoms and AEs; and (5) use of rescue medications.

### **2.4.3 Exploratory Objectives**

The exploratory objectives are as follows:

- To investigate whether the efficacy of extended-release propranolol in the reduction of the pain index varies according to participants' polymorphisms including, but not limited to three other genetic regions: 1) the *COMT* promoter area; 2) adrenergic receptor  $\beta 2$  (*ADRB2*) gene; and 3) the adrenergic receptor  $\beta 3$  (*ADRB3*) gene.
- To investigate whether the efficacy of extended-release propranolol in the reduction of the pain index varies according to various phenotypic characteristics.
- To collect and archive biospecimens for future biological and statistical analyses.

## **2.5 Study Outcome Measures**

### **2.5.1 Primary Outcome Measures**

The primary endpoint will be a weekly mean pain index, representing the arithmetic mean of daily pain index values during the week prior to the study visit. The pain index will be computed during analysis as the product of the pain intensity score, reported on a 0-100 numeric rating scale (NRS), multiplied by the pain duration score, reported on a 0-100 percentage scale, each as reported in the Daily Symptom Diary. The weekly mean pain index will be computed for the week prior to randomization and for each week during the treatment phase. The weekly mean pain index will be calculated if a participant completes at least 4 of the 7 daily reports of pain intensity and duration during the 7-day period prior to the visit. When there are fewer than 4 daily reports, the weekly mean pain index will be considered missing.

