## 4 STUDY ENROLLMENT AND WITHDRAWAL

### 4.1 Participant Inclusion Criteria

A participant must meet all of the following inclusion criteria to be eligible for initial enrollment and randomization:

- 1) Provides a signed and dated informed consent form
- 2) Is between 18 and 65 years of age (inclusive; male or female and any race or ethnicity)
- 3) Meets diagnostic criteria for TMD, Group II: Masticatory Muscle Disorders, 1A: Myalgia
- 4) Has experienced facial pain for at least 3 months
- 5) Has experienced facial pain for at least 10 days of the last 30 days
- 6) At Screening and Baseline Visit (Visit 0), reports an average pain intensity rating over the past week of  $\geq 30$  on a numerical rating scale (0-100)
- 7) At randomization (Visit 1), has satisfactorily completed at least 4 entries per week in the Daily Symptom Diary within the preceding week and reported an average pain intensity score  $\geq 30$  on a numerical rating scale (0-100) or reports a rating of average daily pain intensity of  $\geq 30$  on the same scale on at least 3 days over the past week
- 8) If taking a prescription medication (with the exception of prescription formulations of NSAIDs, acetaminophen, and aspirin) episodically (or as needed) for the management of pain, agrees to discontinue its use prior to or at the Screening and Baseline Visit
- 9) If taking a prescription medication daily for the management of pain, agrees to continue the daily use of the medication throughout the study
- 10) If taking an over-the-counter pain medication daily, agrees to continue the daily use of the medication throughout the study
- 11) Agrees to not commence any new prescription medication for the management of pain throughout the study
- 12) Agrees to not commence any injection therapy for pain (e.g., tender or trigger point injections, steroid injections) during the course of the study
- 13) Agrees to not use acupuncture, biofeedback, or transcutaneous electrical nerve stimulation (TENS) for the management of pain during the course of the study
- 14) Agrees to not commence occlusal splint therapy during the course of the study
- 15) Agrees to continue use of splint therapy if commenced more than 30 days previously

---

- 16) Females agree to limit consumption of alcohol to no more than 7 drinks\* and males agree to limit consumption of alcohol to no more than 14 drinks\* a week for the duration of the study

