## **6.2 Screening and Baseline Visit 0 (Day -21 to Day-7)**

The following procedures and assessments will be conducted up until the time of screen failure:

- 1) Obtain consent for study participation
- 2) Obtain consent to store biological specimens for future studies
- 3) Obtain signed Health Insurance Portability and Accountability statement (as applicable)
- 4) Collect demographic information
- 5) Obtain medical history
- 6) Administer the AUDIT Questionnaire
- 7) Administer the Smoking Questionnaire
- 8) Administer the Symptom Inventory
- 9) Record concomitant medications
- 10) Record specified concomitant therapies
- 11) Collect physical measurements
- 12) Collect vital signs
- 13) Perform a urine pregnancy test in female participants of childbearing potential
- 14) Administer the Fibromyalgia Questionnaire
- 15) Perform the manual tender point examination
- 16) Administer the SF-McGill Pain Questionnaire
- 17) Perform TMD examination
- 18) Review eligibility criteria
- 19) Perform pressure and heat pain tests (baseline data)
- 20) Dispense outcome measure questionnaires as shown in Schedule of Events
- 21) Dispense new Daily Symptom Diaries
- 22) Schedule next visit

---

23) Perform a screening ECG

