### **7.1.10 Daily Symptom Diary**

The participants will be asked to complete the Daily Symptom Diary at the end of each day starting at Visit 0 and ending at Visit 5. Participants who complete at least 4 out of the 7 entries per week at Visit 1 will be considered eligible for study participation. The diary requests information about the participant’s pain intensity (reported on a 0-100 numeric rating scale) and duration (reported on a 0-100 percentage scale), fatigue, sleep, and somatic symptoms. The participants will complete a Daily Symptom Diary on a new paper form each week of the study, as described in the MOP. The participants will return paper-based diaries either by mail or in person at study visits. Compliance with the Daily Symptom Diary will be defined as completion of at least 4 daily entries within 7 days. Any noncompliance found during Visits 2 through 5 will be reported as protocol deviations.

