### 11.4.1 Analysis of the Primary Hypothesis

The primary statistical analysis to evaluate the primary hypothesis will use all data from the intention-to-treat analytical sample in a linear mixed model. During the analysis of the primary hypothesis, treatment allocation will be masked (i.e., groups will be labeled A and B). Treatment allocation will be unmasked for further analyses.

---

The dependent variable will be the participant's change in the weekly pain index, computed as the weekly pain index at the follow-up visit (i.e., at Visit 2, Visit 3, or Visit 4) minus the Visit 1 weekly pain index. Explanatory variables will comprise fixed factors and a continuous covariate. The fixed factors will include the following: (a) treatment allocation (two categories) (b) visit sequence (three categories); (c) interaction of treatment allocation and visit sequence (two dummy variables); and (d) covariates of study site (three categories), sex (two categories) and race/ethnicity (probably three categories: non-Hispanic White, non-Hispanic Black, and other/multiple racial or ethnic groups – the final number of conditions will be dictated by the frequency distribution of race/ethnicity in the study sample). The baseline score collected at Visit 1 will be the continuous covariate, modeled as a fixed effect. The study participant will be modeled as a random factor.

In a linear mixed model containing all predictor variables including the interaction terms for visit and treatment allocation, the primary treatment effect will be tested at Visit 4. The null hypothesis of no treatment effect will be rejected if the P-value at Visit 4 is  $\leq 0.05$ . For descriptive purposes (and regardless of the P-value for efficacy at Visit 4), efficacy estimates at each visit (2, 3 and 4) will be described in terms of adjusted means and 95% confidence intervals.

If the propranolol treatment arm has a greater reduction in the weekly pain index than the placebo arm at Visit 4, a threshold of "responder analysis" will be undertaken to estimate the odds of at least a 30% reduction, relative to Visit 1, in the pain index at Visit 4. Likewise, another threshold of responder analysis will describe the odds of experiencing at least a 50% reduction. These estimates will be calculated from a logistic model in which the dependent variable is a binary variable that dichotomizes the change score at the appropriate threshold (i.e.,  $\geq 30\%$  or  $\geq 50\%$ ).

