## APPENDIX A: SCHEDULE OF EVENTS

Study Phase: Clinic Visit: Study Day:	Pre-screening a	Screening and Baseline	Randomization and Treatment (1 week titration, 8 weeks maintenance, and 1 week taper)				Follow-Up
		V0	V1 b	V2	V3	V4	V5
	≤ 28 days prior to V0	7 to 21 days prior to V1	0	7 (+ 3)	35 (± 7)	63 (+ 6)	77 (+ 7)
Procedure							
Contact Information	x						
Prescreening Interview Script	x						
Informed Consent c		x					
Eligibility Review	x	x	x				
AUDIT Questionnaire		x					
Smoking Questionnaire		x					x
Alcohol Consumption per week			x	x	x	x	x
Demographic Information		x					
Medical History and Review	x	x	x	x	x	x	x
Concomitant Medications		x	x	x	x	x	x
Concomitant Therapies		x	x	x	x	x	x
Dispense New Daily Symptom Diaries		x	x	x	x	x	
Adverse Event Review			x	x	x	x	x
Collect Daily Symptom Diaries			x	x	x	x	x
Assess Compliance with Daily Symptom Diaries			x	x	x	x	x
Collect Confidence in Treatment Outcome			x				
Randomization			x				
Dispense Study Drug			x d	x	x	x	
Collect Study Drug Container(s)				x	x	x	x
Assess Compliance with Study Drug				x	x	x	x

Study Phase: Clinic Visit: Study Day:	Pre-screening a	Screening and Baseline	Randomization and Treatment (1 week titration, 8 weeks maintenance, and 1 week taper)				Follow-Up
		V0	V1 b	V2	V3	V4	V5
	≤ 28 days prior to V0	7 to 21 days prior to V1	0	7 (+ 3)	35 (± 7)	63 (+ 6)	77 (+ 7)
Clinical Examinations and Tests							
Physical Measurements		x					
Vital Signs		x	x	x	x	x	x
Urine Pregnancy Test (females)		x	x	x	x	x	x
Manual Tender Point Exam		x					
TMD Examination		x			x	x	
Heat and Pressure Pain Tests		x			x	x	
12-Lead ECG		x					
Blood Draw			x			x	
Schedule Next Visit	x	x	x	x	x	x	
Outcome Measure Questionnaires							
Symptom Inventory		x	x	x	x	x	x
Fibromyalgia Questionnaire		x					
Headache Questionnaire e			x				
SF-McGill Pain Questionnaire		x		x	x	x	x
Graded Chronic Pain Scale e			x		x	x	
SF-12 Health Survey v2 e			x		x	x	
Jaw Functional Limitation Scale e			x		x	x	
Perceived Stress Scale e			x		x	x	
Hospital Anxiety and Depression Scale e			x		x	x	
Pittsburgh Sleep Quality Index e			x		x	x	
Headache Impact Test (HIT-6) e			x		x	x	
SCL-90R Somatization Scale e			x		x	x	
Coping Strategies Questionnaire-Revised e			x				

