8.3.1 Primary Efficacy Analyses

The primary statistical analysis to evaluate the primary hypothesis will use all data from the ITT analytical sample in a linear mixed model. Mixed models will be used to analyze the treatment effect at V4 (Proc Mixed, SAS, version 9.4 or greater, SAS Institute, Inc., Cary, North Carolina). The mixed model will include the net change in the mean pain index as the dependent variable. The model's independent variables will include fixed effects for site, sex, race-ethnicity, the

Version 3.0 Page 14 of 25

mean pain index at V1 (as a baseline covariate), visit (V2, V3 and V4), treatment allocation (active versus placebo), and a visit by treatment interaction. Participants will be included as a random effect in the mixed model. The mixed model will be run twice assuming either a compound symmetry or an unstructured variance structure. The mixed model achieving the lowest Akaike information criterion will be selected as the best model and used for reporting of results. The model's denominator degrees of freedom will be adjusted for any possible effects of sample imbalances due to any missing values using Kenward Roger's method in SAS. For descriptive purposes (and regardless of the P-value for efficacy at Visit 4), efficacy estimates at each visit (2, 3 and 4) will be described in terms of adjusted means and 95% confidence intervals.

If there is a treatment effect, then "responder analyses" will be performed to compare the responder status of the treatment allocation groups. Participants will have their binomial responder status classified at both the 30% and 50% response threshold levels. The odds ratios of treatment group allocation on the responder status of participants at both the 30% and 50% threshold levels will be estimated using logistic regression with covariate adjustments for site and V1 weekly mean pain index. The odds ratio for the effect of treatment allocation on responder status for both the 30% and 50% threshold levels will be reported with their 95% confidence limits and their associated P-values.

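### The pain-index models adjust for one pre-randomization diary week although up to three are collected, which gives up a modest amount of precision at Visit 4

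*Protocol*

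**What the plan says.** - **Baseline.** Protocol 2.5.1: "The weekly mean pain index will be computed for the week prior to randomization and for each week during the treatment phase". A weekly value needs at least 4 of 7 daily reports. SAP Table 8-1 repeats this and defines net change as the V2, V3 or V4 index minus the V1 index.
- **Diary.** Protocol 7.1.10 asks participants to "complete the Daily Symptom Diary at the end of each day starting at Visit 0 and ending at Visit 5". Appendix A places Visit 0 at "7 to 21 days prior to V1". The diaries are collected at Visit 1 (Protocol 6.3.1).
- **Entry.** Under inclusion criterion 7 (Protocol 4.1), at Visit 1 the participant "has satisfactorily completed at least 4 entries per week in the Daily Symptom Diary within the preceding week and reported an average pain intensity score" of at least 30, or has ratings of at least 30 on 3 or more days. This is the same week that supplies the baseline.
- **Adjustment.** Protocol 11.4.1: "The baseline score collected at Visit 1 will be the continuous covariate, modeled as a fixed effect". SAP 8.3.1 lists the V1 index as the only pain-history term in the primary mixed model. The 30% and 50% responder logistic models adjust for site and the V1 index.

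Neither document uses the earlier diary days in an efficacy model.

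**The concern.** One week of a fluctuating pain index measures a person's usual level with noise. Here the week is also selected, because a participant enters only if that week is painful enough. Earlier diary days carry further information on the usual level and lie outside the Visit 1 selection, although Visit 0 has its own pain threshold. Leaving them out makes the baseline covariate weaker than the collected data allow. The Visit 4 standard error is then larger than it need be, and the adjusted responder odds ratios are less sharp.

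The gene-by-treatment model extends the primary model and inherits the same covariate. Its stated power is only 61%.

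**Working it through.** **Inputs from the documents.** 200 randomized 1:1, SD of the baseline index 1190, net changes of -810 and -270 (difference 540), alpha 0.05 (Protocol 11.2); Visit 0 to Visit 1 gap of 7 to 21 days (Appendix A).

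**Not in the documents.** The correlation between diary weeks and the distribution of the gap. Both are assumed below.

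**1. The plan's own figure.** With 100 per arm, SE = 1190 × √(2/100) = 168.3.
- Difference 540: 540/168.3 = 3.21; Φ(3.21 − 1.96) = 89.4% two-sided.
- Haplotype-weighted difference 0.3×1080 + 0.5×540 + 0.2×0 = 594: 594/168.3 = 3.53; Φ(3.53 − 1.96) = 94.2%. This reproduces the stated 94%.

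Neither figure takes credit for baseline adjustment.

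**2. Does the single qualifying week bias the comparison?** Trials were simulated with selection on that week and no treatment effect (4,000 per setting). The mean change was -102 to -301 in each arm. The baseline-adjusted between-arm estimate stayed within about 4 points of zero, and type I error was 4.9% to 5.5%. So there is no bias.

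**3. Precision when everyone has extra weeks.** Let ρ be the correlation of a baseline week with the Visit 4 week, and r_b that between baseline weeks. For the mean of k baseline weeks, the residual variance is SD² × (1 − R²), with R² = ρ²k / (1 + (k − 1)r_b). If a share s of the variance is stable between persons and short-term noise correlates c between adjacent baseline weeks, then ρ = s and r_b = s + (1 − s)c.

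| s | c | r_b | 1 − R², k=1 | 1 − R², k=2 | Ratio |
|---|---|---|---|---|---|
| 0.5 | 0.4 | 0.70 | 0.750 | 0.706 | 0.94 |
| 0.5 | 0 | 0.50 | 0.750 | 0.667 | 0.89 |
| 0.8 | 0.4 | 0.88 | 0.360 | 0.319 | 0.89 |
| 0.8 | 0 | 0.80 | 0.360 | 0.289 | 0.80 |

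A second week for everyone therefore cuts residual variance by 6% to 20%. In the first row the residual SD goes from 1031 to 1000, and power for 540 goes from 96.0% to 96.9%.

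**4. Gaps spread evenly over 7 to 21 days.** Only 8 of the 15 possible gaps (14 to 21 days) contain a second whole week. Simulating V1 week plus run-in mean against V1 week alone, with s of 0.5-0.8 and c of 0-0.4, gives ratios of 0.895 to 0.969, a cut of about 3% to 10%. A separate calculation over the same range of s gave 3% to 18%, hence 3-10% or somewhat more.

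**5. If correlation decays over time.** With weekly correlation falling geometrically, a two-week mean baseline cut the standard error by 0.6% to 4.3%. In variance that is 1 − 0.994² = 1.2% to 1 − 0.957² = 8.4% if everyone has two weeks. Scaling crudely by 8/15 gives about 0.6% to 4.5%. With a stable share of only 0-20%, the cut for evenly spread gaps is about 0-4%.

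**6. In participants.** A variance cut v is worth 200 × (1/(1 − v) − 1): about 6 participants at 3% and 22 at 10%.

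**The case against.** A reader might infer that regression to the mean from the qualifying week spoils the treatment comparison. The documents do not support that. The tested quantity is the between-arm difference at Visit 4 with the V1 index in the model. Analysing change is then equivalent to analysing the Visit 4 score, and the natural fall is equal in expectation in both arms. It affects how within-arm changes and absolute responder rates are read, not the test.

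A reader might also infer that a second covariate would repair responder status. It would not: status is still measured against the V1 week, and no one is reclassified. The adjusted odds ratio becomes sharper. These models also run only if a treatment effect is found.

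The single week has a rationale. It matches the endpoint's 7-day window. Inclusion criterion 8 lets participants stop episodic prescription analgesics as late as Visit 0, so early run-in days may partly reflect that change. Diary completion is an entry requirement only for the last week, so earlier days may be sparse, and a mean over one to three weeks is not equally reliable in everyone. These points stand as limits. They argue for keeping the V1 week in the model, not for ignoring the earlier days.

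The strongest remaining objection is that the gain rests on assumed correlations and may be close to nil. That is correct, and the range above includes it.

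**Conclusion.** The point holds as one of efficiency only. The models use one pre-randomization week when more may be available, and the Visit 4 contrast and its type I error are sound either way. The precision given up is modest: roughly 0-4% of Visit 4 residual variance if correlation mostly decays, and 3-10% or somewhat more if at least half the variance is stable between persons. Both ranges assume gaps spread evenly over 7 to 21 days. If most gaps were near 7 days the gain would be close to zero, and with longer gaps it would be larger. The direction is clear, but the size cannot be derived from the documents.

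**What to change.** In SAP 8.3.1, before unmasking:

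- Keep the V1 week for the change score and as a covariate.
- Add a second covariate: the mean daily pain index over all available pre-randomization diary days from the most recent Visit 0 to Visit 1. Saying most recent covers the repeated Visit 0 allowed in the Appendix A footnote.
- Where no earlier entries exist, this mean equals the V1 index, so it creates no missing values.
- Use the same covariate in the 30% and 50% responder logistic models.
- State that the gene-by-treatment model inherits it.
- Record the addition in SAP section 11, which now reports no changes from the protocol.

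The cost is one degree of freedom and one derived variable from diaries already collected. The downsides are unequal reliability across participants, early days that may reflect stopping episodic analgesics, and no gain for a 7-day gap. If the team prefers to leave the primary model unchanged, the same covariate can be prespecified as a sensitivity analysis, but the primary test then gains nothing.

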### **2.5.2 Secondary Outcome Measures**

DNA analyses of blood samples will be conducted to identify polymorphisms in the gene that encodes catechol-O-methyltransferase (*COMT*). Assessments of pain intensity (NRS 0-100) and pain duration (0-100 percentage scale) from the Daily Symptom Diary will be used as secondary outcomes. Additional assessments of clinical pain, heat and pressure pain, jaw function, health status, emotional status, participant ratings of global improvement, sleep, somatic symptoms, AEs, and the use of rescue medication will be made by questionnaires and examinations, as described in Section 7.1.

### 3 STUDY DESIGN OVERVIEW

Two hundred participants with chronic TMD recruited at 3 clinical sites, will be randomized in a 1:1 ratio to propranolol or placebo in a parallel-group, blinded clinical trial. Participants will be limited to age 18 – 65 years because pharmacokinetic data are not available for patients over 65 years for extended-release propranolol hydrochloride; standard propranolol drug clearance is decreased and half-life increased in older populations. Additionally, with aging, arthralgia, osteoarthritis, and osteoarthritis become more prevalent TMD diagnoses than myalgia; propranolol will not be effective for these types of TMD.

Participants will attend 6 clinic visits over a period of 12 to 15 weeks (Figure 1). The study should be completed in 3 years, with participant recruitment occurring during years 1 and 2.

Prescreening will be performed either in the clinic or over the telephone, and potentially eligible participants will be scheduled for a Screening and Baseline Visit (Visit 0). During Visit 0, participants will be consented and evaluated for eligibility, and information including demographics, medical history, and concomitant medications will be collected. Additionally, participants will be assessed for pain, health status, jaw function, emotional functioning, sleep, and somatic symptoms, among other measures. Procedures will include clinical examinations and tests and the dispensation of various questionnaires, all of which are listed in the Schedule of Events (Appendix A).

At Visit 1, participants who show compliance with the Daily Symptom Diary (at least 4 daily entries within 7 days) and meet the pain score and all other eligibility requirements will be randomized to propranolol or placebo and will begin a 10-week drug treatment phase that is divided into 1 week of drug titration, 8 weeks of drug maintenance, and 1 week of drug tapering. During that period, Visits 2-4 will take place, and many of the baseline assessments will be repeated. The final study visit, Visit 5, will occur 1 week after drug tapering ends and 2 weeks after Visit 4.

The primary endpoint will be the weekly pain index derived from the Daily Symptom Diary. Efficacy will be evaluated as the difference between the propranolol and placebo arms in the mean change in the pain index during treatment. In addition, variation in efficacy will be compared between groups of participants classified according to polymorphisms in the coding region of the *COMT* gene.

Enrollment will not be stratified according to *COMT* genotype because in the pilot study sample, the haplotype variants were sufficiently distributed for statistical evaluation of a treatment-haplotype interaction without stratified randomization. In the pilot study, 30% of participants had no copies of the LPS haplotype, 50% had one copy, and 20% had two copies. Stratification by *COMT* genotype would significantly increase the complexity of enrollment and could delay the start of treatment for participants while their DNA test results were pending. The DNA analyses will be conducted after all participants have been enrolled.

